6.3.4.2 Safety

Safety analyses are based on observed values. Any missing safety data including laboratory data will not be imputed. For adverse events (AEs), any events with missing start or stop date will be considered as treatment emergent AEs. For concomitant medication, any medication with missing start or stop dates are considered as Day 1 concomitant medication.

Adverse events with incomplete dates will be categorized as treatment emergent unless there was sufficient specificity to the onset date to document that the event began before the first dose of study medication. No missing dates will be imputed.

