5.3. Medical Management Guidelines

5.3.1. Adverse events

Adverse events or abnormal test findings must be followed until the event (or its sequelae) or the abnormal test finding resolves, stabilizes at a level acceptable to the Sponsor/Investigator and/or returns to baseline values.

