8.4.2. Non-Serious AEs

All non-serious AEs that occur during the designated study period from consent through EOS must be assessed and recorded on the source documents and eCRF, regardless of causal relationship to the investigational product.

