10.4.4.1. Adverse Events

The Medical Dictionary for Regulatory Activities (MedDRA) dictionary will be used for coding AEs. An AE (classified by preferred term) occurring during the investigational product treatment period will be counted as a treatment emergent AE (TEAE) either if it is not present at baseline or if it is present at baseline but increased in severity during the treatment period.

The number (percentage) of subjects reporting TEAEs for each preferred term will be tabulated by system-organ class, by system-organ class and severity, and by system-organ class and relationship to investigational product. If more than one event occurred with the same preferred term for the same subject, the subject will be counted only once for that preferred term using the most severe or related occurrence for the summary by severity, or relationship to investigational product, respectively.

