3.1. Screening Period (Days –14 to –1)

All screening laboratory tests will be collected and shipped to the Central Laboratory, with the exception of urinalysis and pregnancy test, which will be done in-house at the participating institution's laboratory using the testing materials provided by the Central Laboratory. The results of all screening laboratory tests should be reviewed prior to enrollment. If results do not confirm subject eligibility or suggest any contraindication to treatment with inclisiran, and/or other required ancillary medication(s), the subject must not be enrolled.

The following procedures will be performed within 14 days prior to randomization:

- Informed consent
- Assessment of inclusion and exclusion criteria
- Demographics and medical history
- Pregnancy test (performed locally, using central laboratory supplies) (women of childbearing potential only)
- Physical examination (including height, weight, and waist circumference)
- Vital signs (blood pressure and heart rate) (Section 3.8.3)
- 12-lead ECG
- Fasting lipid profile/biomarkers (Section 3.9)
- Central clinical laboratory (limited serum chemistry, hematology and coagulation) (Section 3.8.8)
- Urinalysis (performed locally, using central laboratory supplies)
- Previous and concomitant medications
- AE/SAE reporting (beginning from time of consent)
- Pharmacogenetics (stored samples, only if separate con Appendix C)
 been signed) (Protocol

Central laboratory blood draws should be performed after all other screening tests have been confirmed. Results must be available before the start of investigational product injection on Day 1 to confirm subjects meet eligibility criteria (Protocol Section 4.2 and 4.3). Please refer to Section 3.8.8 and Section 3.9 for details of laboratory tests performed during the screening period.

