6.4.8.1. Adverse Events

The Medical Dictionary for Regulatory Activities (MedDRA) dictionary (v20.1) will be used for coding AEs. An AE (classified as preferred term) occurring during the treatment period will be counted as a treatment emergent AE (TEAE) either if it is not present at Day 1 before treatment or if it is present before treatment but increased in severity during the treatment period.

The following summary tables will be presented:

• Overall Summary of TEAEs

^{*} Post baseline LDL-C subgroup included for PCSK9 summary table only.

- TEAEs by SOC and PT
- TEAEs by PT
- Common (2% within either treatment group) by PT
- TEAEs by SOC, PT, and Severity
- TEAEs by SOC, PT, and Relationship to Study Drug
- Related TEAEs by SOC, PT, and Severity
- Treatment Emergent Serious AEs (TESAEs) by SOC and PT
- TESAEs by PT
- TESAEs by SOC, PT, and Severity
- TESAEs by SOC, PT, and Relationship to Study Drug
- Related TESAEs by SOC, PT, and Severity
- TEAEs Leading to Withdrawal of Study Treatment by SOC and PT
- TEAEs with a Fatal Outcome by SOC and PT

If more than one event occurred with the same preferred term for the same subject, the subject will be counted only once for that preferred term using the most severe or related occurrence for the summary by severity, or relationship to study drug, respectively.

For common (2% within either treatment group) TEAEs, serious TEAEs and TEAEs leading to withdrawal of study medication, risk ratios along with 95% confidence intervals will be presented to compare treatment groups with respect to risk.

The following additional adverse events (Refer to Appendix 5, Additional Adverse Events Investigations) will also be assessed:

- 1. Adverse Events at the Injection Site
- 2. Hepatic events
- 3. Renal events
- 4. Hypersensitivity
- 5. Neurological events and Neurocognitive disorders
- 6. Ophthalmological events

Clinically relevant TEAEs at the injection site will also be tabulated. See Appendix 6 for a list of clinically relevant injection site preferred terms.

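### SAP 6.3.4.2 makes an adverse event treatment-emergent because its stop date is missing, even when onset is known to precede first dose and the event did not worsen

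*SAP*

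**What the plan says.** SAP 6.3.4.2 (Safety) has two rules for AE dates.

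- **First paragraph:** "any events with missing start or stop date will be considered as treatment emergent AEs". No exception is attached.
- **Second paragraph:** events with incomplete dates are treatment-emergent "unless there was sufficient specificity to the onset date to document that the event began before the first dose of study medication". It then rules out imputing dates, so an absent stop date stays absent.

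The definition itself is elsewhere. SAP 6.4.8.1 counts an AE occurring in the treatment period as treatment-emergent "either if it is not present at Day 1 before treatment or if it is present before treatment but increased in severity" during that period. Protocol 10.4.4.1 has the same concept: "either if it is not present at baseline or if it is present at baseline but increased in severity during the treatment period". Neither gives the stop date any role.

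Neither document says which rule prevails. The SAP addendum revises concomitant medications, subgroups, laboratory tests, the statin/LMT effect and the washout model, and leaves 6.3.4.2 as it was.

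**The concern.** Defaulting to treatment-emergent is sensible when onset is unknown. It has no such justification when onset is known to be pre-dose and only the end of the event is undocumented, because the end date says nothing about whether the event began or worsened on treatment.

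The affected events can occur. Collection starts before dosing: "All non-serious AEs that occur during the designated study period from consent through EOS must be assessed and recorded" (Protocol 8.4.2), and SAP 3.1 likewise starts AE reporting at consent. Follow-up need not run to resolution. Under Protocol 5.3.1 it may end once the event "stabilizes at a level acceptable to the Sponsor/Investigator", so an unresolved event can lack a stop date.

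TEAE status feeds the incidence tables and the comparison between arms in SAP 6.4.8.1: "For common (2% within either treatment group) TEAEs, serious TEAEs and TEAEs leading to withdrawal of study medication, risk ratios" are presented with 95% confidence intervals. Two programmers working from this SAP could produce different TEAE tables, each with text to support it.

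**Working it through.** The plan gives no figure to reproduce. The check applies each rule to the same set of cases.

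| Case | 6.3.4.2, para 1 | 6.3.4.2, para 2 | SAP 6.4.8.1 / Protocol 10.4.4.1 |
|---|---|---|---|
| A. Complete pre-dose onset (say Day -5), no stop date, no worsening | TEAE | Exempt if 'incomplete dates' covers a wholly absent stop date; otherwise silent | Not TEAE |
| B. Partial onset, clearly pre-dose (month known, first dose in the following month), no stop date, no worsening | TEAE | Exempt | Not TEAE |
| C. Onset missing, no stop date | TEAE | TEAE | Cannot be settled; default needed |
| D. Onset missing, stop date known and pre-dose | TEAE | TEAE (only the onset date can exempt) | Not TEAE |
| E. Onset after first dose, no stop date | TEAE | TEAE | TEAE |
| F. Pre-dose onset, worsened on treatment, no stop date | TEAE | Default lifted or silent; the definition decides | TEAE |

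In case A the definition gives the same answer whatever happened after onset. If the event had ended before Day 1, it did not occur in the treatment period. If it continued, it was present before treatment and did not worsen. Paragraph 1 therefore conflicts with the definition in cases A and B. It conflicts directly with paragraph 2 only in case B.

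**Size.** The documents give no counts of missing dates, so the number of affected records cannot be computed. The following shows scale only.

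- From the documents: screening lasts at most 14 days, participation is about 554 days, and 482 subjects were enrolled.
- Assumed: AE onset is uniform over time; 1 to 4 AEs per subject; 10% to 50% of pre-dose AEs have no stop date and no worsening.
- Pre-dose share of follow-up: 14/554 = 2.53%.
- Share of AE records affected: 2.53% × 10% = 0.25%, to 2.53% × 50% = 1.26%.
- AE records: 482 × 1 = 482, to 482 × 4 = 1,928.
- With pre-dose onset: 482 × 14/554 = 12.2, to 1,928 × 14/554 = 48.7.
- Changing class: 12.2 × 10% = 1.2, to 48.7 × 50% = 24.4, that is, about 1 to 24 records over both arms and all preferred terms.

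Uniform onset could understate this. Urinalysis and the neurological examination are done before the Day 1 injection and their abnormalities are reportable as AEs, but the documents do not say how many would be entered as medical history instead.

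**Direction.** Suppose arms of equal size have a and b subjects with a term, a > b, and the rule adds k subjects to each. The risk ratio changes by (a+k)/(b+k) − a/b = k(b − a)/[b(b+k)], which is negative. With a < b the change is positive. Either way the ratio moves toward 1. Equal k is an expectation, which holds because these events precede treatment in a randomized trial.

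**The case against.** The strongest reply is that 6.3.4.2 is a fallback for deficient dates and was never meant to override a known onset. On that view paragraph 2 qualifies paragraph 1, and a sensible programmer would reach the right answer. Part of this stands. A reader might infer that paragraph 1 contradicts paragraph 2 for every documented pre-dose onset, and the text does not support that. For a complete onset, paragraph 2 either does not apply, because it concerns incomplete dates, or reads naturally as the exception. What does not stand is the claim that the fallback is harmless as written: it names the stop date as sufficient on its own, and the SAP nowhere subordinates it to 6.4.8.1.

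Second, if the database holds 'ongoing' as a status, an unresolved event is not missing a date and almost nothing changes. This is a fair point. The documents do not settle it, so the effect could be close to zero.

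Third, counting doubtful events as treatment-emergent is conservative for incidence. That is true when onset is doubtful, and the default should be kept there. It is not true of comparisons when onset is known to be pre-dose, because events that cannot be due to treatment dilute a contrast between arms.

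A reader might also infer that the rule favours one arm or visibly shifts particular risk ratios. Neither follows. The rule applies alike to both arms. The few records would be spread over many preferred terms, and each subject counts once per term. Serious TEAEs are the least exposed, since SAP 3.6 has ongoing SAEs followed to resolution.

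**Conclusion.** The point holds as a drafting error with a real but small consequence. The conflict with the TEAE definition is clear from the text and needs no assumption. The conflict within 6.3.4.2 is clear only for partial onsets that are plainly pre-dose.

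The effect is over-counting of TEAEs in both arms and a slight pull of risk ratios toward 1. Its size rests on unknowns: how 'ongoing' is stored, how many AEs began in screening, and how many of those lack a stop date. The figure of about 1 to 24 records depends wholly on the stated assumptions and is not an estimate from trial data. The risk ratios are descriptive, and efficacy conclusions are untouched. The rule should still be corrected, because it is wrong as written and cheap to put right.

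**What to change.** In SAP 6.3.4.2:

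1. Delete 'or stop' from the AE sentence and state that an AE lacking only a stop date is treated as ongoing.
2. State that AEs are classified by onset or worsening under 6.4.8.1.
3. Keep the treatment-emergent default only when onset is missing or too incomplete to place it before first dose, and no known stop date shows that the event ended before first dose. This also resolves case D.

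The addendum already postdates database lock and unblinding, so a change now would too. Record it as a dated post-unblinding clarification and report, by arm, how many AEs change class between the two rules. The addendum sets a precedent for showing both versions, with its two Hy's Law summaries in section 2.3.

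The cost is a few sentences, a change to the derivation code and one count table. No new data are needed.

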6.4. Statistical Analyses

6.4.1. Subject Disposition

Subject disposition will be summarized as follows:

- The number of subjects who signed the informed consent form, are screen failures, are randomized, are treated (Safety Population), completed the study or who discontinued early along with reasons for early discontinuation will be summarized overall and by site for all screened subjects.
- The number of subjects in each analysis population along with reasons for exclusion from each analysis population will be summarized by treatment group for all randomized subjects.
- The number of subjects who complete the study or who discontinued early along with reasons for early discontinuation will be summarized by treatment group for each analysis population.
- The duration on study (number of days from the first date of treatment to the date of last recorded contact/participation date in the database) will be summarized by treatment for each analysis population.
- The number of subjects who are screened, screen failures, and randomized will be summarized by country and site for all screened subjects.
- The number of subjects in each treatment group will be summarized by country and site for each analysis population.

Completers are defined as a subject who completes the Day 540 visit.

A summary of inclusion/exclusion criteria will be provided by treatment group for all screened subjects and for the ITT population.

A summary of the number of subjects by visit will be provided by treatment group for each analysis population.

6.4.2. Protocol Deviations

The number and percentage of subjects with any protocol deviations will be summarized by treatment group. The protocol deviation categories are provided below.

- Subjects with at least one protocol deviation
- Inclusion and/or exclusion criteria violation
- Laboratory assessments not drawn at Day 1, Day 510 or Day 540 (EOS) visits

• Mis-dosing for any reason other than subject safety or withdrawal

- Prohibited concomitant medication / Change in baseline statin or other lipid-lowering therapy dose
- SAE form not reported to MDCO within 24 hours
- Informed consent not signed prior to study entry

6.4.3. Demographic and Background Characteristics

Subject demographics including age, age category (<65 years vs ≥65 years; 18 to <50, 50 to <65, 65 to <75, ≥75 years), race, gender, ethnicity, country, and baseline characteristics such as body height, weight, BMI, waist circumference, current use of statins or other lipid-modifying therapies (yes, no), status of statin intolerance, baseline eGFR, genetic testing results, and baseline diabetes status based on HbA1c and fasting glucose will be summarized by treatment group using the ITT, FAS, mITT, and Safety populations.

Medical history (targeted medical history, other medical history, and medical history of statin intolerance) will be summarized by treatment group using the ITT, FAS, mITT and Safety populations.

6.4.4. Study Drug Exposure

Study drug administration will be summarized overall by treatment group and by dosing visits (including, missed doses, and injection site location) for safety population.

6.4.5. Concomitant Medications

Summaries of each prior (pre-baseline, defined as medication stopped 1 day before first dose date of study medication) medication and concomitant (Day 1 or later, any medications started or continued after study medication on Day 1 are considered as Day 1 concomitant medication) medications will be provided by treatment group for ITT, FAS, mITT, and safety population. Additional summaries will be provided for lipid modifying therapy use. Medications will be coded using the World Health Organization (WHO) drug dictionary (B3 WHO DDE+HD Sep 2017). Subjects will be counted only once within each period by medication.

The statin intensity (low, moderate, high) will be defined by clinical review of the data according to American College of Cardiology/American Heart Association (ACC/AHA) classification of high intensity and based on the specific statin drug name, dose (unit), and frequency recorded in the data. The high intensity group will include simvastatin 40 mg. A shift table for lipid modifying therapy statin intensity from baseline to Day 540 (EOS) will also be provided. The statin intensity of the last statin taken on or prior to Day 540 (EOS) will be used for the post-baseline statin.

6.4.6. Efficacy Analysis

The ITT population will be the primary population for the efficacy analysis. Efficacy analyses will also be performed for the FAS and mITT populations as supportive analyses.

6.4.6.1. Primary Efficacy Endpoints

The co-primary endpoints for this study are:

• Percentage change in LDL-C from baseline to Day 510

• Time adjusted percentage change in LDL-C from baseline after Day 90 and up to Day 540. This is the average percentage change in LDL-C from baseline over the period after Day 90 and up to Day 540.

Note: The time adjusted percentage change in LDL-C from Baseline after Day 90 and up to Day 540 analysis reflects LDL-C effect at a steady state. As such, this analysis assesses the effect on LDL-C levels seen with a more chronic dosing regimen. The Day 90 dose is the start of the 6 monthly dosing regimen.

The statistical hypotheses for the co-primary endpoint of the percentage change in LDL-C from baseline to Day 510 are as follows:

H01: The difference (inclisiran minus placebo), between subjects treated with inclisiran 300mg and placebo in the least squares mean percentage change in LDL-C from baseline at Day 510 = 0.

HA1: The difference (inclisiran minus placebo), between subjects treated with inclisiran 300mg and placebo in the least squares mean percentage change in LDL-C from baseline at Day 510 < 0.

The statistical hypotheses for the co-primary endpoint of the time adjusted percentage change from baseline after Day 90 and up to Day 540 are as follows:

H02: The difference (inclisiran minus placebo), between subjects treated with inclisiran 300mg and placebo in the least squares mean time adjusted percentage change in LDL-C from baseline after Day 90 and up to Day 540 = 0.

HA2: The difference (inclisiran minus placebo), between subjects treated with inclisiran 300mg and placebo in the least squares mean time adjusted percentage change in LDL-C from baseline after Day 90 and up to Day 540 < 0.

The family-wise type I error rate is controlled at a two-sided significance level of alpha=0.05 by using a nested testing procedure. The percentage change in LDL-C from baseline to Day 510 will be tested first. If the null hypothesis is rejected at a two-sided significance level of alpha=0.05 and superiority of inclisiran over placebo is claimed, then the time adjusted percentage change in LDL-C from baseline after Day 90 and up to Day 540 will be tested, also at a two-sided significance level of alpha=0.05.

The primary endpoints will use a reflexive LDL-C approach: either calculated LDL-C (based on the Friedewald formula) will be used, or if the calculated LDL-C is less than 40 mg/dL or triglycerides are greater than 400 mg/dL, or calculated LDL-C is missing, directly measured (using ultracentrifugation) LDL-C will be used if it is available.

Percentage change in LDL-C from baseline to Day 510

Missing values will be imputed for LDL-C after a reflexive approach using the multiple imputation (100 total imputed datasets) washout model specified in Appendix 2. The percentage change in LDL-C at each visit will be calculated after the missing data imputation has been performed.

The primary analysis will be conducted on the ITT population and based on an ANCOVA model on the percentage change in LDL-C from baseline to Day 510 on each multiply imputed dataset

(100 total). The model will include the fixed effect of treatment group and baseline LDL-C as a covariate.

Treatment effects from these 100 ANCOVA analyses will then be combined using Rubin's Method via the SAS PROC MIANALYZE procedure. The difference in the least squares means between treatment groups and corresponding two-sided 95% confidence interval will be provided for hypothesis testing.

See Appendix 2 for more details on this analysis.

Time adjusted percentage change in LDL-C from baseline after Day 90 and up to Day 540.

A control-based pattern-mixture model (PMM), following the methods described in Ratitch and O'Kelly (2011), will be utilized to explore the possibility of data missing not at random (MNAR) for subjects who discontinued the study. For subjects who discontinued the study without any further follow-up data, their missing values after study discontinuation will be imputed under the assumption that their outcome would be similar to those in the placebo group with similar background characteristics. For subjects who did not discontinue the study, their intermittent missing values will be imputed based on the MAR assumption. Multiple imputations will be used to account for uncertainty in the imputation process and results from the imputed datasets will be combined using Rubin's method [Rubin, 1987]. See Appendix 3 for more details on this analysis.

The primary analysis will be conducted on the ITT population and based on a mixed-effects model for repeated measurements (MMRM) on the percentage change in LDL-C from baseline over all visits on each multiply imputed dataset (100 total). The model will include fixed effects for treatment, visit, baseline value, and the interaction between treatment and visit. The Restricted Maximum Likelihood (REML) estimation approach will be used with the covariance structure set as "Unstructured" (refer to Appendix 1 for further details on the MMRM).

The time adjusted percentage change in LDL-C from baseline after Day 90 and up to Day 540 will be calculated from the MMRM. Linear combinations of the estimated means after Day 90 and up to Day 540 will be used to compare treatment effects. Note that Day 90 will be excluded from the MMRM.

Treatment effects from these 100 MMRM analyses will then be combined using Rubin's Method via the SAS PROC MIANALYZE procedure. The difference in the least squares means between treatment groups and corresponding two-sided 95% confidence interval will be provided for hypothesis testing.

